**APPENDICES**

## **GLOSSARY of Terms and Abbreviations**

AE	Adverse Event
AR	Adverse Reaction
ASR	Annual Safety Report
CA	Competent Authority
CI	Chief Investigator
CRF	Case Report Form
CRO	Contract Research Organisation
DMC	Data Monitoring Committee
EC	European Commission
GAfREC	Governance Arrangements for NHS Research Ethics Committees
ICF	Informed Consent Form
JRMO	Joint Research Management Office
NHS REC	National Health Service Research Ethics Committee
NHS R&D	National Health Service Research & Development
Participant	An individual who takes part in a clinical trial
PI	Principal Investigator
PIS	Participant Information Sheet
QA	Quality Assurance
QC	Quality Control
RCT	Randomised Controlled Trial
REC	Research Ethics Committee
SAE	Serious Adverse Event
SDV	Source Document Verification
SOP	Standard Operating Procedure
SSA	Site Specific Assessment
TMG	Trial Management Group
TSC	Trial Steering Committee

## SUMMARY/SYNOPSIS

Short Title	Evaluation of tailored electronic reminders on compliance with removable orthodontic retention
Methodology	
Mixed methods design
 
Part 1: A Randomized Controlled Trial
 
Part 2: Qualitative investigation using one-to-one interviews

Research Sites	The Dental Hospital, Barts Health NHS trust
Objectives/Aims	
The primary objective is to analyse the effect of electronic reminders on compliance with removable orthodontic retention.
 
The secondary objectives are to assess the subjective levels of retainers wear and to measure upper/lower anterior irregularity and transverse dimensions. We also aim to explore patients' experience with electronic reminders in a related qualitative element.

Number of Participants/Patients	Based on sample size calculation, patients referred into the orthodontic Department, Royal London Hospital will be recruited.
Main Inclusion Criteria	
Inclusion Criteria:
 
 
- Aged 12 to 21 years;
 
- Planned for removable retention with Essix-type vacuum-formed retainers
 
- Fit and well and on no medication;
 
- In the permanent dentition.
 

Statistical Methodology and Analysis (if applicable)	Data analysis will involve descriptive and analytical statistics performed using

	
software (SPSS, New York, NY, USA). Assessment of the reliability of the measures used in the study will be tested by assessing agreement between the measurements (Bland and Altman, 1986). Baseline characteristics will be summarised to ensure that all groups are similar with respect to potential confounding variables. Inferential statistics will be used to compare differences in the duration of appliance wear between the treatment groups. If the data follows a normal distribution, linear regression analysis will be used to assess the influence of retention protocol on the main outcome. This technique will allow for confounding factors including degree of crowding pre-treatment; age; and gender. The level of statistical significance will be pre-specified at <math>P<0.05</math>.
 
Transcripts of the interviews will be entered in NVivo 10 TM qualitative data analysis software (QSR International) and anonymised for analysis.
 
The Framework approach will be used to analyse the qualitative data (Gale et al., 2013). This approach facilitates the thematic analysis of qualitative data in a structured way around the key questions in the topic guide.

Proposed Start Date	May 2016
Proposed End Date	24 months after recruitment of the final participant.
Study Duration	24 months

## INTRODUCTION

**The introduction acts as the starting point for outlining the background and justification for the research, with clear concise objectives which have scientific merit and relate to existing literature.**

Orthodontic retention following treatment is essential to resist the tendency of teeth to return to their pre-treatment positions. Removable retainers worn on full- or part-time basis are acceptable retention procedures. However, removable retention places an onerous premium on excellent long-term compliance.

Within the biomedical literature there is ample evidence alluding to the effectiveness of electronic and telecommunication systems in improving adherence to long-term use of medications (Reidel et al., 2008; Armstrong et al., 2009; Boland et al., 2014), self-monitoring of chronic conditions (Logan et al., 2007) and in terms of attendance at appointments (Gurol-Uranci et al., 2013). Specifically tailored approaches have proven particularly effective (Stacy et al., 2009). There is, however, no reported usage of these approaches within orthodontics. Moreover, electronic reminders to improve compliance with removable retention regimes among orthodontic patients have not been explored.

The primary aims of this study is to analyse the effect of electronic reminders on compliance with orthodontic retention at 3, 6 and 12 months following removal of fixed appliances.

The secondary aims are to assess the subjective levels of retainers wear, and to measure upper/lower anterior irregularity and transverse dimensions. We also aim to explore patients' experience with electronic reminders in a related qualitative element.

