## TRIAL OBJECTIVES

**Primary /Secondary Objectives to be outlined as defined by the Primary/Secondary Endpoints which are also to be listed here.**

The primary objective is to explore the effect of electronic reminders on compliance with orthodontic retention.

The secondary objectives are to assess the subjective levels of retainer wear and to measure upper/lower anterior irregularity and transverse dimensional changes during the retention phase. We also aim to explore patients' experience with electronic reminders in a related qualitative element.

- Primary Endpoint

Objective level of compliance with retainer wear at 6 months (T3) of orthodontic retention.

- Secondary Endpoints

Objective level of compliance with retainer wear at 3 months (T2) and 12 months (T4) of orthodontic retention.

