## **Study Design / Plan – Study Visits**

Subjects will be recruited for inclusion at a routine adjustment appointment prior to planned removal of the appliances in the Orthodontic Department at Institute of Dentistry, Barts and The London School of Medicine and Dentistry, UK. Following removal of the appliances, consenting participants will be randomly allocated to one of two groups by computer-generated random allocation. Allocation will be concealed from the treating clinician using of an opaque sealed envelope system. Study models will be available for all participants following removal of the appliances (T1).

Participants in both groups will have follow-up scheduled for 3 (T2), 6 (T3) and 12 (T4) months following removal of the appliances. All participants will be instructed to wear vacuum-formed (Essix-type) retainers on a full-time basis for 6 months, followed by night-time wear for a further 6 months (Gill et al., 2007). A Thera-Mon™ micro-electronic timer will be integrated within the upper Essix-type retainer. All participants will be given standard advice at each recall visit. If any patient from both groups fails to attend their routine retainer check visit, another appointment will be arranged and posted through Royal Mail.

Participants in the intervention group will receive tailored electronic reminders. The frequency and content of the reminders will be informed by the qualitative findings of an ongoing trial, but are likely to include an intra-oral photograph taken pre-treatment and following removal of the active appliances, instructions on the necessary duration of retention, advice on maintenance of retainers, departmental details, advice on appropriate management for appliance breakages, and delineation of the implication of suboptimal retainer wear. Participants in the control group will not receive additional reminders.

Treating clinicians will be kept blind to the study group.

All patients failing an appointment will be sent another. Those wishing to withdraw from the trial may do so at any point without affecting continuing care with records taken at the point of withdrawal from the study with data analysis on an intention to treat basis.

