## STUDY PROCEDURES

Participants will be recruited by treating clinicians at Institute of Dentistry, Barts and The London School of Medicine and Dentistry. Potentially eligible participants will be given an information sheet detailing the study and its objectives at the visit prior to removal of their fixed appliances. Participants agreeing to be involved will be asked to sign a consent form for inclusion in the study at the following visit. Patients under 16-18 years can consent for themselves only if they were deemed mature to make a decision, this will be decided by the CI and PI. Otherwise, the parent will be asked to consent for their child.

Following removal of the appliances, consenting participants will be randomly allocated to one of two groups by computer-generated random allocation. Allocation will be concealed from the treating clinician using of an opaque sealed envelope system. Standard orthodontic study models will be available for all participants following removal of the appliances (T1).

Participants will then be reviewed at 3, 6 and 12 months for regular retainer checks and collection of records i.e. study models and microsensor readings.

One-to-one interviews will be undertaken in a confidential non-clinical areas. Interviews will continue until data saturation has been achieved characterized by a lack of new emergent themes.

All documents including models will be securely held in a locked office, photos will also be stored on an encrypted trust computer.

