### Schedule of Assessment (in Diagrammatic Format)

Please use a table format to detail the schedule of assessments that the participant will undergo at each visit (see example below).

Assessment	Randomization	Retention phase	Treatment phase	End of Study	Follow up visits
Enrollment, written information sheet, consent	Computer-generated random allocation. Allocation will be concealed from the treating clinician using of an opaque	3-monthly retainer check visits and records collation (study models and timer readings)	One-to-one interview with subset of recruited participants	End of retainer check visits	24 months

	sealed envelope system				
--	------------------------	--	--	--	--

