### **End of Study Definition**

Follow-up of retention procedures will be undertaken over a 24-month period. The final retainer checks will be undertaken at 12 and 24 months in keeping with standard orthodontic practice. The study will be completed following the 24-month visit.

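### Do the three visits in the introduction's primary aim, and the study end at 24 months, leave the primary test or the end of the trial undefined?

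*Combined protocol and SAP*

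**What the plan says.** **Primary time point.** In the Introduction the primary aim is to "analyse the effect of electronic reminders on compliance with orthodontic retention at 3, 6 and 12 months following removal of fixed appliances". Trial Objectives has a labelled primary endpoint, "Objective level of compliance with retainer wear at 6 months (T3) of orthodontic retention", followed by a secondary endpoint, "Objective level of compliance with retainer wear at 3 months (T2) and 12 months (T4) of orthodontic retention". The Sample Size Calculation and Statistical Methods sections name no visit. Statistical Methods sets one significance level of 0.05 and gives no rule for several tests.

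**Length of follow-up.** Under Study Design / Plan, "Participants in both groups will have follow-up scheduled for 3 (T2), 6 (T3) and 12 (T4) months following removal of the appliances". Study Procedures agrees: "Participants will then be reviewed at 3, 6 and 12 months for regular retainer checks and collection of records". The Schedule of Assessment table instead has "3-monthly retainer check visits and records collation (study models and timer readings" among its entries and puts 24 months in its follow-up column. The End of Study Definition places the final checks at 12 and 24 months and adds: "The study will be completed following the 24-month visit". The Synopsis gives a study duration of 24 months and an end date "24 months after recruitment of the final participant".

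**The concern.** A reader who starts at the Introduction meets three time points under the primary aim, one 0.05 level and no multiplicity rule. On that reading, success could be claimed at whichever visit happened to cross the threshold, and the true error rate would exceed the stated 5%.

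The second worry is the extra year. No listed endpoint, timer reading or wear instruction belongs to 24 months, yet that visit closes the study, 12 months (24 − 12) after the last scheduled outcome. The Synopsis adds a puzzle. If 24 months is the length of the whole study and the study also ends 24 months after the last recruit, then 24 − 24 = 0 months remain to enrol 84 people.

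**Working it through.** **1. Does the sample size fit one test or three?**

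Inputs from Sample Size Calculation: 31% non-compliance, a difference of 25%, power 80%, level 0.05, 34 per group. Assumptions: the 25% is absolute (31% against 6%), the test is two-sided and allocation is 1:1.

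Unpooled formula: n = (z₀.₉₇₅ + z₀.₈₀)² × [p₁(1−p₁) + p₂(1−p₂)] / (p₁−p₂)²

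- (1.960 + 0.842)² = 7.85
- 0.31 × 0.69 + 0.06 × 0.94 = 0.2139 + 0.0564 = 0.2703
- 7.85 × 0.2703 / 0.0625 = 33.9, so 34 per group and 68 in all.

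This is the plan's own figure, and the arcsine formula also gives 34. The pooled-variance formula gives 37, so the match depends on the variant.

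With the level split three ways (0.05/3 = 0.0167), the unpooled formula needs 46 per group (92) and the pooled formula 50 (100). At 34 per group, power at 0.0167 would be 66% (unpooled) or 61% (pooled). The stated number is that of a single comparison at the full 0.05.

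**2. What would three unadjusted tests cost?**

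If the tests were independent and any one could win: 1 − 0.95³ = 1 − 0.857 = 14.3%. The visits reuse the same participants and timers, so independence is not realistic. Simulating three equally correlated z statistics, with rejection if any |z| > 1.96, gives:

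| Assumed correlation | Type I error |
|---|---|
| 0.3 | 13.6% |
| 0.5 | 12.5% |
| 0.7 | 10.9% |
| 0.9 | 8.4% |

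The documents give no correlation. These rates apply only if all three visits are primary and one success is enough. No section states such a rule, and Trial Objectives excludes it by ranking the visits.

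**3. Do the statements on follow-up exclude each other?**

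| Section | What it fixes |
|---|---|
| Study Design / Plan; Study Procedures | visits at 3, 6 and 12 months; Study Procedures ties records to them; neither calls 12 months the last visit |
| Schedule of Assessment | retainer checks every 3 months; 24 months under follow-up |
| End of Study Definition | final checks at 12 and 24 months, as standard practice; completion after 24 |
| Synopsis | end 24 months after the last recruit; duration 24 months |

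The sections that state an end of study agree on 24 months. A last outcome at 12 months and a routine check closing the study at 24 can coexist. If the Synopsis duration is per participant, it matches the end date and the zero-recruitment puzzle disappears. Taken literally, the three-month interval would add a 9-month visit, but no endpoint uses one, and three other sections list 3, 6 and 12 months.

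**The case for a change.** The strongest case for acting is that nothing says which section governs. The primary objective carries no time point, Statistical Methods speaks only of the main outcome, and the sample size names no visit. A 68 computed at 0.05 is also what planners would get if they had simply overlooked multiplicity, so the match in step 1 supports the single-test reading without proving it. Every error rate in step 2 exceeds 5%, and the cure is a few words. On follow-up, the visit that closes the study is missing from the visit plan, and its status as trial visit or routine care is not stated.

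Some of this stands. The Introduction does not match the endpoint section, the table's interval is loose, and the purpose of the 24-month check is unstated. The inferential consequence does not stand. Trial Objectives is where endpoints are defined, and it separates primary from secondary by visit; an introductory aim spanning three visits can sit beside one primary endpoint. Claiming a primary success at 3 or 12 months would mean overriding that section.

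The burden of a second year is also weaker than it looks. The End of Study Definition calls the check standard practice, and Finance and Funding says participants attend routine retainer checks.

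**Conclusion.** No change to the plan follows. The primary comparison is compliance at 6 months, tested once at 0.05, with 34 per group evaluable; 3 and 12 months are secondary. Aligning the Introduction with Trial Objectives would leave the endpoint, level, sample size and conclusion as they are. The 8.4% to 14.3% error range is hypothetical, since it arises only if the endpoint section is ignored, and all but its upper end rests on assumed correlations.

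The 24-month wording is loose rather than shown to be contradictory, provided that the duration is read per participant and the late check as routine care. Both readings are open on the text, though neither is spelled out. Reconciling the visit passages is housekeeping that no result depends on.

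This conclusion rests on Trial Objectives governing the analysis and, for the sample-size support, on an absolute 25-point difference and a two-sided test.

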## TRIAL OBJECTIVES

**Primary /Secondary Objectives to be outlined as defined by the Primary/Secondary Endpoints which are also to be listed here.**

The primary objective is to explore the effect of electronic reminders on compliance with orthodontic retention.

The secondary objectives are to assess the subjective levels of retainer wear and to measure upper/lower anterior irregularity and transverse dimensional changes during the retention phase. We also aim to explore patients' experience with electronic reminders in a related qualitative element.

- Primary Endpoint

Objective level of compliance with retainer wear at 6 months (T3) of orthodontic retention.

- Secondary Endpoints

Objective level of compliance with retainer wear at 3 months (T2) and 12 months (T4) of orthodontic retention.

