### Sample Size Calculation

Based on previous research (Tsimos et al., 2014) alluding to a non-compliance rate of 31% characterized by wear of the appliance for less than 2 hours daily a minimum of 68 participants (34 in each group) is required with a power of 80% to detect a minimum difference of 25% in compliance rates at the 0.05 level of statistical significance. To compensate for a dropout rate of at least 10%, the final number to be enrolled in the trial is 84.

For the second part of the study, Initially, 10 one-to-one interviews will be undertaken. Interviews will continue until data saturation has been achieved characterized by a lack of new emergent themes.

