### Statistical Methods

Data analysis will involve descriptive and analytical statistics performed using software (SPSS, New York, NY, USA). Assessment of the reliability of the measures used in the study will be tested by assessing agreement between the measurements (Bland and Altman, 1986). Baseline characteristics will be summarized to ensure that all groups are similar with respect to potential confounding variables. Inferential statistics will be used to compare differences in

the duration of appliance wear between the treatment groups. If the data follows a normal distribution, linear regression analysis will be used to assess the influence of retention protocol on the main outcome. This technique will allow for confounding factors including degree of crowding pre-treatment; age; and gender. The level of statistical significance will be pre-specified at  $P<0.05$ .

For the second part of the study the Framework approach will be used to analyse the qualitative data (Gale *et al.*, 2013). This approach facilitates the thematic analysis of qualitative data in a structured way around the key questions in the topic.

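### Does the primary endpoint fail because the plan does not say which days of timer data count as compliance at 6 months?

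*Combined protocol and SAP*

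**What the plan says.** Trial Objectives lists a single primary endpoint, "Objective level of compliance with retainer wear at 6 months (T3) of orthodontic retention", with the same measure at T2 and T4 as secondary. Study Design / Plan – Study Visits defines T3 only as the follow-up visit planned 6 months after the appliances come off. It places the measuring device in the retainer ("micro-electronic timer will be integrated within the upper Essix-type retainer") and tells participants to wear the "retainers on a full-time basis for 6 months, followed by night-time wear for a further 6 months". It also says that if a patient "fails to attend their routine retainer check visit, another appointment will be arranged and posted".

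Study Procedures has the 3, 6 and 12 month reviews include "collection of records i.e. study models and microsensor readings", and the Schedule of Assessment repeats this as "records collation (study models and timer readings".

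The Sample Size Calculation takes from previous research a "non-compliance rate of 31% characterized by wear of the appliance for less than 2 hours daily". Statistical Methods compares "the duration of appliance wear between the treatment groups", with linear regression on the main outcome if the data are normal. None of these sections gives a first and last day for the T3 value.

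**The concern.** A duration or a daily rate needs a period, and the plan gives only a visit. Three readings are open: all wear since the appliances were removed, wear since the T2 reading, or wear shortly before the visit. One participant can be compliant under one and non-compliant under another.

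Two features sharpen the point. The wear instruction changes at month 6, exactly at the primary time point. Missed visits are rebooked with no visit window, so a T3 reading taken up to a late visit would include days under the night-time instruction.

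If the period were picked after the wear curves had been seen by group, the choice could influence the primary result. The planned 25-point difference and 80% power would then describe only one of several possible endpoints, and the plan does not say which.

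**Working it through.** **Inputs.** From the Sample Size Calculation: 31% non-compliance, a 25-point difference (so 31% v 6%), 34 per group, 80% power, 0.05 level (two-sided assumed), and the 2 h/day description. From Study Visits: visits at 3, 6 and 12 months, with the wear instruction changing at month 6. Assumed, because the documents give no figures: hours of wear per day, the pattern of stopping, the SD of mean hours, and how late a visit is. Months 0-6 = 365.25/2 = 182.6 days; months 3-6 = 91.3 days.

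**1. The plan's own figure.** Unpooled two-proportion formula: n = (0.31×0.69 + 0.06×0.94)(1.96 + 0.842)²/0.25² = 33.9, so 34 per group, as stated. Power at 34 is 80.1%. The window does not enter this calculation.

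**2. Can the window change an individual's class?** Yes. With 4 h/day in months 0-3 and none afterwards, the mean is (4 + 0)/2 = 2 h/day over months 0-6, which is not below the cut-off, and 0 h/day over months 3-6.

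**3. Does that imply a loss of power?** Take a simple model: wear of h hours a day until permanent stopping at a constant rate. A participant is below 2 h/day in window [s, e] if stopping comes before t = s + (2/h)(e − s).

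- h = 22: t = 99.6 days for months 3-6 and 16.6 days for months 0-6; ratio 1/6.
- h = 8: t = 114.1 and 45.7 days; ratio 0.4.

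The non-compliance rate in the second window is 1 − (1 − p)^ratio, where p is the rate in the window to which the planning rates are attached. Power is Φ(|p1 − p2|/√((p1q1 + p2q2)/34) − 1.96).

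| 31% v 6% attached to | Other window | h = 22 | h = 8 |
|---|---|---|---|
| months 3-6 | months 0-6 | 6.0% v 1.0%, power 20% | 13.8% v 2.4%, power 42% |
| months 0-6 | months 3-6 | 89% v 31%, power above 99% | 60% v 14%, power above 99% |

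For the second row the exponents are 6 and 2.5. The same model gives a large loss or a large gain, and the only difference is which window is taken to match the planning rates. The plan attaches the 31% to no window, so neither row can be preferred.

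The 20% is also a poor approximation. At 6% v 1% about 2 and 0.3 events are expected (34×0.06 and 34×0.01). Exact enumeration gives about 11% for the uncorrected chi-square and about 1% for Fisher's test.

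**4. The analysis as planned.** Statistical Methods compares duration of wear, not the 2-hour classes. For mean hours the months 0-6 difference is (d0-3 + d3-6)/2. With an assumed SD of 5 h and 34 per group:

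- d0-3 = 0 and d3-6 = 3 h: months 0-6 difference 1.5 h, power 24%, against 70% for months 3-6.
- d0-3 = 3 and d3-6 = 1 h: months 0-6 difference 2 h, power 38%, against 13% for months 3-6.

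Again neither window is better in general.

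**5. Late T3.** If T3 is 4 or 6 weeks late and the months 3-6 window runs to the visit, 28/(91.3 + 28) = 23.5% or 42/(91.3 + 42) = 31.5% of its days fall under the night-time instruction. At an assumed 20-22 h/day before month 6 and 8-9 h/day after it, a fully adherent wearer's mean drops by 2.8-3.1 or 3.8-4.1 h/day. That wearer stays far above 2 h/day. The drop biases the group comparison only if lateness differs between arms, and the documents give no sign of that.

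**The case for a change.** The strongest argument for a change is that this is the combined protocol and SAP, so no later plan can be assumed to fill the gap. Trial Committees states that there are none, so no committee would check a window chosen late. Fixing one would cost a sentence. Reminders might also affect attendance, which would make late visits differ by arm.

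Part of this stands. The period is not stated, a cumulative reading is as compatible with the text as one since the previous visit, and it is good practice to settle the period before wear is compared by group.

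The rest does not carry the case. Nothing in the plan provides for choosing the window by its result. A difference in attendance is conjecture, and the delays are assumed. The power losses depend on attaching the planning rates to one window. The argument that the main outcome has no time point is weak, because Trial Objectives names T3 as the sole primary time point. The Introduction's wording of the primary aim at 3, 6 and 12 months is a looser statement that the endpoint list resolves.

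**Conclusion.** No change follows. The observation is correct: the days behind the T3 value are not specified. But this is missing detail, not a faulty rule. Wear since the last reading and wear since appliance removal are both objective summaries of the same timer record, both compare the groups as randomised, and an analyst deriving the variable must and would choose one. The choice alters what is estimated, early and later wear together or later wear alone, without making either comparison invalid.

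The documents allow no estimate of how far the primary result would move. The individual example (4 h/day, then none) shows that the windows can disagree. The group-level figures run in both directions, from 20% to above 99% power against a planned 80%, and rest on assumed wear, stopping and anchoring. The sample size of 34 per group is reproduced and does not depend on the window.

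This conclusion assumes that the period is settled without reference to results by group, and that late T3 visits are similar in the two arms. Figure 1 is not available, but its caption describes participant flow, so it is unlikely to bear on the point.
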